1.0 General Information

***Enter the full title of your study:**

A prospective, randomized analysis of epidural anesthesia using programmed intermittent epidural boluses versus continuous epidural infusion in patients undergoing abdominal surgery.

***Enter the study number or study alias**

PCEA with PIEB versus CEI
 * This field allows you to enter an abbreviated version of the Study Title to quickly identify this study.

4.0 Initial Screening Questions - Updated 2015

(Note: You must answer every question on this page to proceed.)

4.1 * PROJECT SUMMARY: (REQUIRED) Give a brief overview of this project (250 words or less). Tell us what this study is about, who is being studied, and what it aims to achieve. If you have an NIH Abstract, paste it here: Click on the orange question mark to the right for more detailed instructions.

Epidurals are an effective means for providing neuraxial anesthesia and analgesia. Prior studies in labor epidurals have demonstrated that a programmed intermittent bolus application of local anesthesia can improve pain control thus reducing the amount of local anesthetic required as well as improve patient

satisfaction when compared to continuous epidural infusions. The effects of programmed intermittent bolus of epidurals compared to continuous epidural infusions in a surgical setting have yet to be elucidated. Our goal is to evaluate the use of programmed intermittent bolus compared to continuous epidural infusion in a surgical patient population. We plan to enroll patients already undergoing surgery under the enhanced recovery after surgery (ERAS) pathways. ERAS pathway surgeries include colorectal, gynecologic, surgical oncology to name a few. The primary endpoints of the study will be the total local anesthetic consumption and total opioid consumption as surrogate markers for the quality of epidural anesthesia. Secondary endpoints are pain scores and functional measurements, patient satisfaction, and incidence of hypotension .

4.2 * HUD DEVICE: (REQUIRED) Does this application involve a Humanitarian Use Device (HUD):

- No
- Yes, and it includes a research component
- Yes, and it involves clinical care ONLY

4.3 * TYPE OF RESEARCH: (Click the Help link for definitions and guidance): (REQUIRED)

- Biomedical research
- Social, behavioral, educational, and/or public policy research
- Hybrid - includes aspects of BOTH types of research (check this option if your research is mainly social /behavioral but also involves specimen collection or blood draws to look at biological measures)

4.4 * SUBJECT CONTACT: (REQUIRED) Does this study involve ANY contact or interactions with participants:

- Yes (including phone, email or web contact)
- No (limited to medical records review, biological specimen analysis, and/or data analysis)

4.5 * RADIATION EXPOSURE: Does your protocol involve any radiation exposure to patients/subjects EITHER from standard care OR for research purposes (e.g., x-rays, CT-scans, DEXA, CT-guided biopsy, radiation therapy, or nuclear medicine including PET, MUGA or bone scans): (REQUIRED)

- Yes
- No

4.6 * RISK LEVEL: (REQUIRED) What is your estimation of the risk level, including all screening procedures and study activities (Help Text updated 9/13):

- Minimal risk
- Greater than minimal risk

4.7 * REVIEW LEVEL: (REQUIRED) Requested review level (Click on the orange question mark to the right for definitions and guidance):

- Full Committee
- Expedited
- Exempt

4.11 * CLINICAL TRIAL: (REQUIRED) Is this a clinical trial? According to The World Health Organization (WHO) and the International Committee of Medical Journal Editors (ICMJE) a clinical trial is:

- Any research study that prospectively assigns human participants or groups of humans to one or more health-related interventions to evaluate the effects on health outcomes.

ICMJE requires registration of a clinical trial in a public database (such as ClinicalTrials.gov) prior to enrollment, for eventual publication of results in member biomedical journals. Guidance: Public Law

110-85 requires that all investigators who perform an *applicable clinical trial* must ensure that the trial is registered on a government web site called ClinicalTrials.gov. The FDA requires registration for "applicable clinical trials," defined as follows:

- For any trials of drugs and biologics: controlled clinical investigations, other than Phase 1 investigations, of a product subject to FDA regulation.
- For trials of biomedical devices: controlled trials with health outcomes of devices subject to FDA regulation, other than small feasibility studies, and pediatric post-market surveillance.

For additional information on the ClinicalTrials.gov registration process at UCSF and the definition of a clinical trial for purposes of registration, visit the ClinicalTrials.gov section of the UCSF Clinical Research Resource HUB.

Yes No

Clinical Trial Registration

"NCT" number for this trial:

Pending

If you don't yet have the NCT#, type 'Pending.'

4.12 * CLINICAL TRIAL PHASE (REQUIRED) Check the applicable phase(s) (Help Text updated 9/13):

- Phase I
- Phase II
- Phase III
- Phase IV

4.13 * INVESTIGATOR-INITIATED: (REQUIRED) Is this an investigator-initiated study:

Yes No

4.14 SCIENTIFIC REVIEW: If this study has undergone scientific or scholarly review, please indicate which entity performed the review (check all that apply):

- Cancer Center Protocol Review Committee (PRC) (Full approval is required prior to final CHR approval for cancer-related protocols.)
- CTSI Clinical Research Services (CRS) Advisory Committee
- CTSI Consultation Services
- Departmental scientific review
- Other:

4.15 * STEM CELLS: (REQUIRED) Does this study involve human stem cells (including iPS cells and adult stem cells), gametes or embryos:

- No
- Yes, and requires CHR and GESCR review
- Yes, and requires GESCR review, but NOT CHR review

4.16 * FINANCIAL INTERESTS: (REQUIRED) Does the Principal Investigator and/or one or more of the key study personnel have financial interests related to this study:

Yes No

5.0 Funding

5.1 * **FEDERAL FUNDING: (REQUIRED)** Is this study currently supported in whole or in part by Federal funding, *even by a subcontract*, OR has it received ANY Federal funding in the past:

Yes No

5.2 * **DoD INVOLVEMENT: Is this project linked in any way to the Department of Defense (DoD): (REQUIRED)**

Yes No

5.3 **SPONSORS: Identify all sponsors and provide the funding details. If funding comes from a Subcontract, please list only the Prime Sponsor:**

External Sponsors:

NOTE: It is no longer necessary to add the A or the P Number. iRIS now allows you to link the proposal to the study (see below)!

View Details	Sponsor Name	Sponsor Type	Awardee Institution	Contract Type:	UCSF RAS "P number" or eProposal number	UCSF RAS System Award Number ("A" + 6 digits)
--------------	--------------	--------------	---------------------	----------------	---	---

No Sponsor has been added to this IRB Study

If the funding is coming through UCSF and you don't know the A or P number, you can search the eProposal side for the contract or grant (this does NOT replace adding the sponsor by name above):

Project Status	Proposal Number	Project Title	Principal Investigator
----------------	-----------------	---------------	------------------------

No Projects are Linked to this IRB Study

Other Funding Sources and Unfunded Research - Gift, Program, or Internal Funding (check all that apply):

- Funded by gift (specify source below)
- Funded by UCSF or UC-wide program (specify source below)
- Specific departmental funding (specify source below)
- Unfunded (miscellaneous departmental funding)
- Unfunded student project

6.0 Sites, Programs, Resources, and External IRB Review

6.1 **UCSF AND AFFILIATED SITES (check all that apply):**

- UCSF (including Laurel Heights and all the other sites outside the main hospitals)
- Parnassus
- Mission Bay
- China Basin
- Mount Zion
- Helen Diller Family Comprehensive Cancer Center
- Langley Porter Psychiatric Institute
- San Francisco General Hospital (SFGH)
- SF VA Medical Center (SF VAMC)
- Blood Centers of the Pacific (BCP)
- Blood Systems Research Institute (BSRI)
- Fresno Community Medical Center
- Gallo
- Gladstone
- Jewish Home
- Institute on Aging (IOA)
- SF Dept of Public Health (DPH)

6.2 LOCATIONS: At what locations will study visits and activities occur:

UCSF Bakar Cancer Hospital

6.3 OFF-SITE PROCEDURES: Will any study procedures or tests be conducted off-site by non-UCSF personnel:

Yes No

6.4 RESEARCH PROGRAMS: Check any UCSF research programs this study is associated with:

- Cancer Center
- Center for AIDS Prevention Sciences (CAPS)
- Global Health Sciences
- Immune Tolerance Network (ITN)
- Neurosciences Clinical Research Unit (NCRU)
- Osher Center
- Positive Health Program

6.5 * CTSI CRS SERVICES: (REQUIRED) Will this study be carried out at one of the UCSF Clinical Research Services (CRS) units or utilize CRS services:

Yes No

6.6 * MULTI-CENTER TRIAL: (REQUIRED) Is this a multicenter research trial? By multi-center trial, we mean a study where the protocol is developed by an industry sponsor, consortium, a disease-group, etc., who then selects sites across the nation or in different countries to participate in the trial. The local sites do not have any control over the design of the protocol.

Yes No

6.7 OTHER SITE TYPES: Check all the other types of sites not affiliated with UCSF with which you are cooperating or collaborating on this project: Do NOT check any boxes below if this is a multi-center clinical trial, UCSF is just one of the sites, and neither UCSF nor its affiliates are the coordinating center.

- Other UC Campus
- Other institution
- Other community-based site
- Foreign Country
- Sovereign Native American nation (e.g. Navajo Nation, Oglala Sioux Tribe, Havasupai, etc.)

6.10 * RELYING ON AN EXTERNAL IRB: Does this application include a request to rely on an a central IRB (other than the NCI CIRB) or an external IRB (UC, commercial, or institutional): (REQUIRED)

Yes No

7.0 Research Plan and Procedures

7.1 This new consolidated section requests information about:

- Hypothesis
- Aims
- Study Design
- Background and Significance
- Preliminary Studies
- Procedures
- Statistical Methods
- References

Later sections include:

- Drugs and Devices
- Sample Size, Eligibility, and Subjects
- Recruitment and Consent
- Risks and Benefits
- Data and Safety Monitoring Plan
- Confidentiality, Privacy and Security
- Financial Considerations
- Qualifications of Personnel
- Other Approval and Registrations

7.2 HYPOTHESIS: Describe the hypothesis or what the study hopes to prove (Help Text updated 9/13):

Null hypothesis: There is no difference in total local anesthetic and opioids required when comparing patients receiving epidural anesthesia using either programmed intermittent epidural boluses or continuous epidural infusions following abdominal surgery.

7.3 AIMS: List the specific aims:

The aim of this study is to prove the superior efficacy of programmed intermittent bolus administration of epidural medications compared to traditional continuous infusions in providing adequate post-operative analgesia and patient satisfaction in a surgical patient population.

7.4 DESIGN: Briefly describe the study design (e.g., observational, interventional, randomized, placebo-controlled, blinded, cross-over, cross-sectional, longitudinal, pharmacokinetic, etc.):

This is a prospective, randomized controlled study of programmed intermittent bolus administration of local anesthetic in epidural anesthesia compared to traditional continuous infusions for patients undergoing surgery as part of the enhanced recovery after surgery pathway.

As part of the UCSF Enhanced Recovery After Surgery (ERAS) pathway, all patients routinely treated with thoracic/lumbar epidural anesthesia for post-operative analgesia. The planned investigation does not change its approach, but compares solely two different modalities how epidural medications are administered. The study ends when the catheters are removed which is most often on post-operative day two, but can be later in case the patient may still benefit from epidural anesthesia. During the duration of the treatment with epidural anesthesia, enrolled patients will be randomized to receive either programmed intermittent bolus or continuous epidural administration of the local anesthetic ropivacaine (0.0625%) with fentanyl (2ug/ml). In addition to this maintenance administration of local anesthetic, the patient are also able to apply additional (demand) boluses of epidural medication by pressing a button. This technique, called patient- controlled epidural anesthesia (PCEA), is routinely used in all patients with epidural catheters and allows patients to receive additional medication in the event they experience discomfort. If the patients have still pain not covered by epidural anesthesia, they have access to additional RN-administered opioid pain medication. The normally used drugs for such treatment are oxycodone p.o. and hydromorphone i.v. However, other opioids could be used in this context and all opioid use would be quantified using a conversion to oral morphine equivalents. The primary outcomes of the study will be the total amount of local anesthetic administered and opioid requirements (oral morphine equivalents). Secondary outcomes are: numeric pain rating scores (should not be different as patients have access to additional analgesic medication), number of patient attempts to trigger additional PCEA boluses, overall patient satisfaction assessed through validated questionnaires, and incidence of hypotension.

7.5 BACKGROUND AND SIGNIFICANCE: Briefly provide the background and significance of this study (e.g. why is this study needed) (space limit: one half page):

If this is a first in humans study, please summarize the safety data from the animal studies. For pediatric drug or device studies, please identify if this is the first study in pediatric populations.

Programmed intermittent bolusing of epidurals have been shown in the labor analgesia setting to have significantly decreased in total local anesthetic consumption as well as significantly higher overall patient satisfaction scores as compared to traditional continuous infusions. Whether these observations apply to post-surgical analgesia settings and post-surgical populations have yet to be elucidated. Addressing the aforementioned question is of clinical importance as this may represent an avenue for the improvement of post-surgical analgesia that is not dependent on the use of opioid based approaches. The planned investigation would be the first study to investigate the use of programmed intermittent bolusing of epidurals in surgical patient populations and in surgical analgesia.

7.6 PRELIMINARY STUDIES: Briefly summarize any preliminary studies relevant to your proposed research (space limit: one half page):

Prior studies in the use of programmed intermittent epidural bolusing has been in the labor anesthesia literature. Wong et al (2006) showed in a randomized controlled trial that there was significantly less local anesthesia consumption, less requirement for manual rescue bolus, and higher satisfaction scores in the programmed intermittent epidural bolus group compared with the continuous infusion group. Since then numerous other randomized controlled trials were conducted in laboring women and a meta-analysis conducted in 2013 by George et al further supported the observation of less local anesthetic usage and higher maternal satisfaction score in the programmed intermittent bolus group.

7.8 * COMMON RESEARCH ACTIVITIES: Types of research activities that will be carried out. Check all that apply and describe in more detail in the 'Procedures / Methods' section: (REQUIRED)

- Interviews, questionnaires, surveys
- Educational or cognitive tests
- Focus groups
- Observation
- Non-invasive imaging or testing (MRI, EEG, pulse oximetry, etc.)
- Administration of contrast agent
- Imaging procedures or treatment procedures that involve radiation (x-rays, CT scans, CT-guided biopsies, DEXA scans, MUGA or PET scan)

- Biopsy conducted solely for research purposes
- Use of placebo
- Sham surgical procedure
- Collection of data from wearable tech such as Fitbit, Apple Watch, Garmin, motion actigraphs, etc.)
- Fitness tests or other exertion activities
- Use of mobile health apps or other apps
- Social media-based research activities
- None of the above

7.9 * PROCEDURES / METHODS: (REQUIRED)

For clinical research, list all study procedures, tests and treatments required for this study, including when and how often they will be performed. If there are no clinical procedures, describe the research activities.

If some of the activities would occur even if the person were not in the study, as in the case of treatment or tests performed for diagnostic purposes, clearly differentiate between those activities that will be done solely for research purposes and those that are happening as part of routine care.

Examples may include:

- additional scans outside standard clinical diagnosis or monitoring
- additional biopsies to collect tissue for research
- extra clinic visits
- extra lab tests not required for clinical care

If you have a procedure table, attach it to the submission with your other study documents.

All study participants will complete a questionnaire that includes their pain history, an anxiety and depression questionnaire (Hospital Anxiety and Depression Scale) and the WHO Disability Assessment Schedule 2.0 (WHODAS 2.0). Patients will be block randomized to the programmed intermittent bolus group or continuous infusion group. As part of the existing ERAS pathways, all patients will receive a thoracic/lumbar epidural catheter prior to their scheduled surgical procedure depending on the anticipated surgical incision site. Both groups will receive the same standard concentration of local anesthetic (0.0625% ropivacaine) and opioid (fentanyl 2ug/mL) based epidural mix. A total of 8mL of the epidural mix will be administered every hour either as a continuous infusion (8mL/hr) or programmed intermittent epidural bolus (4mL bolus every 30 min) based on the study participant's randomization. The epidural will be started in the OR, prior to the end of the surgical procedure at the discretion of the intraoperative anesthesia provider.

The clinical investigator who enrolled the patient will write the epidural infusion orders. A PACU nurse will be programming the pump following hospital policies. The attending in the acute pain service will be informed about the enrollment of the patient in the study to ensure the pain service has all the information needed to ensure the best pain control to the patient in accordance with the study protocol. The display of the pump will be covered with a removable cover to make sure that the patient will stay blinded about the treatment group. The epidural pumps will subsequently be managed by the acute pain service, not the study investigators. The study protocol allows the reduction of epidural flow rates from 8ml to 6ml/h (from 4ml q30 to 3 ml q30 min in the bolus group) in case of hypotension.

Patients will have the option to administer patient controlled epidural analgesia (PCEA) in addition to the basal rate. For continuous epidural infusion group, they can receive additional 2ml every 15 minutes (lock out period) for a total of 16ml/hr (8ml/hr from continuous infusion and up to 8ml from PCEA). To match the total epidural volume in the programmed intermittent bolus group, they can receive additional 2ml

using a lock out period of 10 minutes. Because 4ml of epidural is bolused every 30 min and a PCEA bolus cannot coincide with the basal bolus doses, the shortend lock out period is necessary to make sure the patient can still receive the same four additional 2ml PCEA boluses as the continuous infusion group.

In addition, patients will be able to receive additional physician manual boluses, IV opioid medications from nursing staff, adjunct medications as per standard UCSF ERAS protocol. Hypotension and itching are some common adverse reactions to epidural analgesia; we will treat and document these episodes as per preexisting UCSF acute pain service epidural protocol.

Outcome measures will be total local anesthetic use (charted by nursing staff each shift as part of routine care), numeric rating scale (charted by nursing staff as part of routine care), total PCEA button presses (recorded on epidural pump), anxiety and functional measures (WHODAS2.0, brief pain inventory, HADS survey) to be measured on post operative day 1 and 2. Incidence of hypotension (charted by nursing staff as part of routine care).

7.10 STANDARD CLINICAL PRACTICE: To what extent, if any, do the planned research procedures differ from the care that people would otherwise receive at this institution or the study site if not being done locally:

The proposed study tries to maintain the care that patients would otherwise receive at UCSF. The differences would be in the use of randomized assignment to programmed intermittent bolus of epidural or continuous epidural infusion. As a measure of the efficacy of the different study arms, additional questionnaires, interviews listed below differ from standard clinical practice.

All other anesthetic interventions, including the placement and use of an epidural catheter, the monitors, safety parameters, availability to pain physicians, supplemental pain medications are consistent with existing standard clinical practice.

7.11 INSTRUMENTS: List all questionnaires, surveys, interview, or focus group guides that will be used for this study:

A brief validated questionnaire (WHO disability assessment schedule 2.0; hospital anxiety and depression score; brief pain inventory) will be administered at the time of enrollment into the study. During each 24-hour period that the patient has the epidural in place, an abbreviated brief pain inventory (abbreviated to the inpatient population) will be administered. At the end of the study, prior to discharge, the patients will be handed another questionnaire to assess the quality of pain control and patient satisfaction using the expanded brief pain inventory. All the aforementioned surveys are previously published and validated questionnaires.

Attach any unpublished instruments in the 'Other Study Documents' section of the Initial Review Submission Packet form after completing the study application. Published instruments should NOT be attached.

7.12 * BIOSPECIMEN COLLECTION: Are you drawing any blood or collecting other biosamples (e.g. tissue, buccal swabs, urine, saliva, hair, etc.): (REQUIRED)

Yes No

7.25 STATISTICAL METHODS: Briefly summarize the methods and types of analyses that will be performed:

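### The local anesthetic primary is an unscaled total, but its effect size (0.6) and 44 per group come from dose per hour; variable catheter time can lower the power.

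*Combined protocol and SAP*

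**What the plan says.** The local anesthetic primary is a total wherever it appears. The project summary (4.1) names "total local anesthetic consumption and total opioid consumption as surrogate markers for the quality of epidural anesthesia". The null hypothesis (7.2) reads "There is no difference in total local anesthetic and opioids required". The design section (7.4) says "The primary outcomes of the study will be the total amount of local anesthetic administered", and the outcome list in 7.9 has "total local anesthetic use (charted by nursing staff each shift as part of routine care".

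No sentence defines the period over which the total accrues. Section 7.4 says "The study ends when the catheters are removed which is most often on post-operative day two, but can be later", from which accrual to catheter removal is inferred. Section 10.13 adds that removal is typically on the morning of day 2 but may be earlier or later. The pump is "started in the OR, prior to the end of the surgical procedure at the discretion of the intraoperative anesthesia provider" (7.9). The outcome list ends with "to be measured on post operative day 1 and 2", which most naturally refers to the questionnaires.

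Section 7.25 compares continuous outcomes by unpaired t-test and mentions no adjustment for duration. Section 9.3 takes its planning figures from labor analgesia as bupivacaine dose per hour: medians of 10.5 mg/h (bolus) and 12.3 mg/h (infusion). It expects a similar effect size of 0.6, derives 44 per group, and raises enrollment to 60 per group to cover incomplete data.

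**The concern.** The outcome and its sample size are on different scales. Both arms are scheduled to receive the same hourly amount, so every additional catheter hour adds drug whichever technique relieves pain better. Spread in catheter time therefore enters the variance of the total but not that of an hourly rate. If 0.6 holds for the rate, mean duration is equal in the two arms, and duration is independent of rate, then 0.6 is too large for the total and 44 per group is too few.

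A second route is possible but neither shown nor quantified: if the technique changes mean catheter time, the total would differ between arms with no difference in analgesic quality, although 4.1 uses it as a marker of that quality.

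The open definition also leaves total, hourly or windowed dose to be chosen later, and 13.2 plans a comparison of outcomes after 44 patients.

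**Working it through.** **1. The plan's own figure.** For d = 0.6, two-sided alpha 0.05 and 80% power, the normal approximation gives n = 2 × (1.960 + 0.842)² / 0.36 = 43.6, so 44 per group. The exact t calculation gives 45. Noncentral-t power at d = 0.6 is 79% with 44 per group and 90% with 60. The arithmetic is right for a measure on which d = 0.6 holds.

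**2. What the pump can deliver.** Ropivacaine 0.0625% is 0.625 mg/mL. The schedule in both arms is 8 mL/h × 0.625 = 5 mg/h. The infusion arm is described as "for a total of 16ml/hr (8ml/hr from continuous infusion and up to 8ml from PCEA", and the bolus arm is matched to it, so the programmed maximum is 16 × 0.625 = 10 mg/h before physician boluses. The reduction allowed for hypotension gives 6 × 0.625 = 3.75 mg/h.

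**3. Model for the total.** Total = hourly rate R × catheter hours T. With c = rho × s_R × s_T:

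Var(total) = μ_R² s_T² + μ_T² s_R² + 2 μ_R μ_T c + s_R² s_T² + c²

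d(total) = (difference in rate × μ_T) / SD(total)

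The difference in rate is set to 0.6 × s_R, so that d = 0.6 holds on the hourly scale.

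**4. Inputs.** Assumed, because the documents do not give them: mean duration 44 h, duration SD 3 to 12 h, rate 7 ± 1.5 mg/h (within the pump limits), equal mean duration in both arms, rho = 0. The difference is 0.6 × 1.5 = 0.9 mg/h, or 0.9 × 44 = 39.6 mg on the total.

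A second set uses the planning figures: mean (10.5 + 12.3)/2 = 11.4 mg/h and implied SD 1.8/0.6 = 3.0 mg/h. That mean exceeds the programmed maximum, so it serves as a check only.

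**5. Worked case, duration SD 6 h.** Var = 7² × 6² + 44² × 1.5² + 1.5² × 6² = 1764 + 4356 + 81 = 6201. SD = 78.7 mg. d = 39.6/78.7 = 0.50.

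**6. Results** (noncentral t, two-sided 0.05)

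| Duration SD | d | Power, 44 per group | Power, 60 per group | Evaluable per group for 80% | Planning figures: power at 44 / 60 |
|---|---|---|---|---|---|
| 0 (hourly rate) | 0.60 | 79% | 90% | 45 | 79% / 90% |
| 3 h | 0.57 | 75% | 87% | 50 | 77% / 88% |
| 6 h | 0.50 | 65% | 78% | 64 | 69% / 82% |
| 9 h | 0.43 | 51% | 65% | 87 | 58% / 72% |
| 12 h | 0.37 | 40% | 51% | 119 | 48% / 60% |

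A simulation of the 7 mg/h case (20,000 trials per setting) agrees to within one percentage point.

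**7. Break-even.** With 60 evaluable per group, the total keeps 80% power up to a duration SD of about 5.5 h (6.7 h on the planning figures). With 50 evaluable the limit is a little over 3 h (about 4 h). A mean duration of 40 to 48 h moves the 60-per-group limit to 5.0–6.0 h (6.1–7.3 h).

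**8. Sensitivity at SD 6 h.** Other assumed rates, from 6 ± 1.5 to 8 ± 1.0 mg/h, give 81% down to 59% power at 60 per group. In the 7 mg/h case at 44 per group, a rate–duration correlation of −0.2, 0 or +0.2 gives 73, 65 or 57%. A correlation below about −0.33 would cancel the loss.

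**The case against.** The word total may be used loosely, to mean scheduled plus demand plus physician boluses rather than undivided by time: 7.5 describes the labor findings as lower total consumption, and 9.3 then represents that literature by mg per hour. The reading is possible, but it does not remove the problem. No section says that the dose is divided by hours, and on either reading the scale and window are left open.

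The power figures rest on assumed inputs. With 60 evaluable per group and a duration SD of 3 h, power is still 87–88%. At 6 h it is between 59 and 82% depending on the assumed rates, and a modest negative correlation recovers part of the loss. This stands: the loss is conditional, and nothing in the documents shows that an SD of 9 or 12 h applies. Against it, the extra patients are meant for incomplete data, so 60 evaluable per group cannot be counted on.

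Moving to mg per hour also does not validate 0.6. That figure still crosses from bupivacaine in labor to ropivacaine after abdominal surgery, and 9.3 gives medians and intervals with no SD or source sample size from which to derive it. This stands too. The change puts the outcome on the scale of its planning figures and removes duration noise; it does not supply the missing support for 0.6.

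A day 1 and 2 window, if one was intended, would not equalize hours, because start and removal times would still vary within it.

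**Conclusion.** The concern holds and should be settled before the interim analysis. Four sections define the local anesthetic primary as a total with no hourly scaling, and the only basis for 0.6 and 44 per group is a dose per hour. Confidence in that mismatch is high.

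The size of the loss is uncertain because the documents give no duration SD. Under the stated assumptions it runs from about 4 percentage points of power at 44 per group (SD 3 h) to about 39 (SD 12 h). If catheter times are nearly uniform, the loss is small. The defect is that the power for a named primary depends on a condition the plan neither states nor supports.

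**What to change.** Before the interim analysis, define the local anesthetic primary as mg ropivacaine per hour of epidural treatment, from pump start to catheter removal. Keep the total as a supportive outcome. Add a sensitivity analysis of mg over a common early window, for example the first 24 h from pump start, with a stated rule for catheters removed sooner. It is needed because the hourly rate to removal still depends on a stop that occurs after randomization, and short catheters can give noisy or inflated rates.

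If the total stays primary, state its accrual window and restate its power with an explicit duration SD. That SD could come from the site's earlier epidurals in similar patients (12.3 mentions prior use) or from pooled trial data not split by arm.

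In either case, report catheter duration and reason for removal by arm, and state the counting window for opioids as well (a secondary point, not quantified here).

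The cost is low: pump start and removal times must be abstracted for each patient. Because local anesthetic is charted per shift, an exact 24 h amount may need the pump log or apportioning of a shift. No clinical care changes.
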